**SUMMARY TABLE**

|                                   |   |
|-----------------------------------|---|
| Title                      | Flexible Intubation Scope vs. Flexible Intubation Scope and Video Laryngoscopy Combination: A Prospective Randomized Clinical Trial  |
| Project Office             | Department of Anesthesiology, Critical Care and [name] Anderson Cancer Center.   |
| Study Size (# of patients) | 120   |
| Study Design               | This study will be a prospective randomized clinical trial.   |
| Primary Objective          | 
 
To compare the rates of difficult Endotracheal Tube (ETT) placement using a Flexible Intubation Scope (FIS) versus a combination of flexible intubation and video laryngoscopy (VL/FIS) in difficult airway management.
 
   |
| Primary Outcome            | 
 
Difficult ETT placement is defined as: (i.) either first intubation time >60 seconds or (ii.) first attempt failure at intubation or (iii.) ease of intubation reported as difficult by provider.
 
  |
| Secondary Objectives       | 
 
To compare the ease of using a flexible intubation scope (FIS) with and without the use of the video laryngoscope (VL)
 
Total time to secure the airway
 
Number of attempts required for intubation
 
Rate of failure at intubation
 
Incidence of desaturation
 
Assessment for hoarseness, sore mouth, neck, or jaw, dysphonia, dysphagia, lip injury, tongue injury, or tooth damage.
 
   |
| Inclusion Criteria         | 
 
Ages <math>\geq</math> 18 years of age
 
All surgical patients with known or suspected difficult airways that meet at least three (3) of the Difficult Airway criteria [Mallampati III-IV, Neck circumference <math>></math> or <math>=</math> 40 cm, Sternomental distance <math><</math> 12 cm, Thyromental distance <math><</math> 6 cm, Mouth opening <math><</math> 4 cm, BMI <math>\geq</math> 35 kg/m^2, Upper Lip Bite Test - ULBT (class III)] or history of radiation to the head or neck area
 
American Society of Anesthesiology (ASA) I-IV
 
Has provided written informed consent
 
 |
| Study Procedures           | 
 
Initial study assessments will be performed in the preoperative holding area. All study interventions will be performed in the operating room prior to the first surgical skin incision. Postoperative assessments will be conducted in PACU.
 
Patients will be randomized to either study group using OnCore. Group A: FIS (control), Group B: VL/FIS (intervention). After the patient provides consent and is enrolled into the study, they will be randomized to a study group. The study team will inform the attending anesthesia
 
  |

|                            |  |
|----------------------------|--|
|                            | 
provider about the group the patient was assigned and the instruments to be utilized during intubation.
 
 
Following induction of general anesthesia and adequate manual ventilation, the anesthesia provider will attempt to successfully intubate the patient utilizing, a FIS or a combination of FIS and VL. No more than 2 intubation attempts shall be made. If necessary, in between intubation attempts, adequate patient ventilation will be performed prior to the next intubation attempt.
 
For both the control and intervention groups, the anesthesia provider will be given the option to secure the airway via oral pathway (passage) according to clinical judgment. If a patient's airway has not been secured within 2 attempts of the respective, allocation treatment, a third attempt will be made utilizing another technique or device (as a rescue attempt) at the discretion of the anesthesia provider. At this point, no further study data will be collected, except of what device was used for the rescue attempt and any potential Adverse Events.
 
   |
| Brief Analysis Plan | 
For Primary Objective:
 A total of 60 patients will be randomized to each intervention arm (a total of n = 120 patients).
 
 
With 60 patients per study arm, a 2-sided chi-square test with alpha = 0.05, and an assumed rate of difficult ETT of 30% on the control arm, then a minimum detectable difficult ETT rate of 10% (an absolute difference of 20 percentage points) would be considered statistically significant (nQuery v7) with power of 80%.
 
For each study arm consisting of 60 evaluable patients (120 patients total), estimated rates of difficult ETT will be provided using exact 95% CI using the method of Clopper-Pearson. For example, a rate of 25% would provide exact 95% confidence interval limits that do not exceed (0.15, 0.38), exact 99% CI limits that do not exceed (0.12, 0.42) using the method of Clopper-Pearson.
 
 
For the Secondary Objective:
 To evaluate ease of use, each of the 3 dimensions described below will be assessed independently. First, the time of intubation will be assessed for distributional assumptions using histograms, stem and leaf plots, and box plots. Descriptive statistics such as the median and range or the geometric mean <math>\pm</math> SD will be used to summarize the data. Second, ordinal data describing the number of attempts will be summarized using the median and range; and third, the
 |

|  |   |
|--|---|
|  | 
number of complications will be summarized using the median and range. For number attempts and complications, frequencies and percentages will be used if the maximum number is small (<math>\leq 4</math> attempts or complications). Comparisons between continuous covariates of interest will be conducted using a t-test, or Wilcoxon rank-sum test if more appropriate. Categorical covariates will be compared using chi-square or Fisher's exact test.
 
Exploratory Analyses:
 
Depending on the distributional assessment of outcomes for each of the 3 items: i) time of intubation, ii) number of attempts, and iii) the number of complications, a total score will be derived for each patient. Each outcome will be translated into a binary scale. For example, starting with intubation time, the completion a procedure within 60 seconds will be assigned a '0', and completion taking more than 60 seconds will assign a '1'. For the number of attempts, we will assign a '0' for a single attempt and a '1' for more than a single attempt. And finally for complications, we will assign a '0' for no complication arising and a '1' for any complications arising. The total score will range from 0 to 3 and will be summarized using frequencies and percentages related to each level of the total score and using the mean score and standard deviation, whichever is more appropriate. Other exploratory outcomes include: Ease of ETT insertion (ranked on a 1 to 5 scale as described in Section 5.4) and will be summarized using descriptive statistics. These exploratory study outcomes will be compared between treatment arms using an independent samples t-tests or chi-square tests. Potential cut-points for these exploratory outcomes may be considered to inform if low versus high scores are associated with select patient outcomes of interest. Cumulative incidence plots will be used to visualize time to intubation, if appropriate. Multiple logistic regression analyses will be conducted to assess the association between any dichotomous outcomes of interest and type of intervention after adjusting for select covariates of interest.
 |
|--|---|

## 1.0 OBJECTIVES

### 1.1 Primary Objective:

- To compare the rates of difficult Endotracheal Tube (ETT) placement using a flexible intubation scope (FIS) versus a combination of flexible intubation and video laryngoscopy (VL/FIS) in difficult airway management.

### 1.2 Secondary Objectives:

- To compare the ease of using a flexible intubation scope (FIS) with and without the use of the video laryngoscope (VL)
- Total time for securing the airway
- Number of attempts required for intubation
- Rate of failure at intubation
- Incidence of desaturation
- Assessment for hoarseness, sore mouth, neck, or jaw, dysphonia, dysphagia, lip injury, tongue injury, or tooth damage.

### 1.3 Exploratory Objective:

- To assess the utility of using a total score for summarizing 3 dimensions that characterize ease of ETT insertion: i) time of intubation, ii) number of attempts, and iii) the number of complications.

## 2.0 BACKGROUND

### 2.1 Difficult airway in patients with head and neck tumors

Head and neck cancers include tumors of the oropharyngeal cavity, larynx, paranasal sinuses, thyroid and salivary glands.[1] A failure to recognize and to properly manage the airway in this population may lead to significant morbidity and mortality. Patients with head and neck tumors have a higher risk of difficult airways compared to the general population (15.75% vs. 2.5%).[7] In the Fourth National Audit Project (NAP4) of the UK; a large population based study of airway complications Woodall et al. discussed the difficult airway in the head and neck population with 39% of major airway complications occurring in patients undergoing head and neck surgery.[3] In several closed claims analysis studies, patients undergoing head and neck surgery consistently rank among the highest group of patients who experienced an adverse airway related event.[4-6] This may be due to the underlying disease or result from the side effects of treatment (i.e. radiation or surgically induced deformities). Oro-pharyngeal tumors may reduce the amount of space in the oropharynx and result in a difficult direct laryngoscopy. The associated obstructive symptoms may lead to difficulty with ventilation, especially after the induction of anesthesia. Tumors outside the airway, such as large thyroid masses, may produce extrinsic compression or distortion of the trachea or larynx. Radiation induced contractures may also lead to reduced mobility of the neck, and of the tissues of the oropharynx. In addition, radiation induced changes of the larynx may reduce visibility and accessibility of the larynx by conventional laryngoscopy. These changes can be associated with reduced ventilation, which could be exacerbated upon induction of anesthesia.

### 2.2 Flexible Intubation Scope

The gold standard of care for intubating patients with known difficult airways is an awake flexible intubation scope (FIS).[7] Flexible fiberscopes have long been used for tracheal intubation, especially in cases of a difficult airway. Some of the advantages of using a Flexible intubation scope (FIS) are that it provides a means to view the glottis in instances where standard intubation methods fail. These include patients with limited mouth opening, an unstable cervical spine, head and neck tumors, and trauma to the airway.

Asleep FISs are often employed in head and neck cases where the intubation may be challenging, but the ability to mask ventilate the anesthetized patient is possible. This saves time due to not needing to topicalize the patient's mucosa and also avoids the discomfort to the patient of an awake intubation. Nevertheless, it still requires a great deal of skill on the part of the anesthesiologist and can actually take just as long or longer to intubate than when doing an awake FIS, due relaxation or collapse of the soft tissues of the airway into the path of the FIS, making the pathway to the trachea more obscured.[9]

Despite its value to management of the difficult airway, FIS has its pitfalls, once the scope is placed in the trachea, advancement of the tube is still a blind process. Collapse of the airway post induction of anesthesia can obstruct the view with the scope even with the use of jaw thrust. The ETT may get caught on the arytenoids and forceful placement may traumatize the airway.

### **2.3 KARL STORZ Intubation Fiberscopes**

The new flexible 5.5 x 65 intubation video endoscope from KARL STORZ provides a better overview of the working area. Similar to the C-MAC® video laryngoscope, the 5.5 x 65 scope delivers clear, pixel-free images without a moiré pattern. The 5.5 x 65 endoscope can be directly connected to the C-MAC® monitor. This enables a changeover to the video laryngoscope in a short time, if necessary. The flexible 5.5 x 65 intubation video endoscope is a further component within the C-MAC® system.

[figure not shown]
### **2.4 Video laryngoscopy**

Video laryngoscopy (VL) is a method of indirect laryngoscopy using camera technology to visualize airway structures. Incorporating a VL in combination with a FIS enhances the technique of FIS by providing a view above the glottis and thus allowing visualization of the ETT as it is advanced into the airway.[12] Also, the VL will help open the oropharynx and improve the view while providing

complete visualization of the FIS. VL has become the recommended method as the preference in patients with suspected difficult tracheal intubation. Advantages of using VL include the elimination of the need to align the airway axes to provide a line of sight, providing a better view of the glottis especially in cases with limited neck extension or mouth opening, serving as an educational tool allowing other providers to view the airway structures, less hemodynamic response to intubation, and decreased risk of esophageal intubation.[10] Aziz et al. report a 92% success rate with the use of VL as a rescue in patients in whom direct laryngoscopy had failed.[11] In a randomized controlled trial comparing different video laryngoscopes to direct laryngoscopy, Yumul et al. found an improved glottic view using VL compared to standard direct laryngoscopy using a laryngoscope.[13] Lenhardt et al. found a 100% success rate of intubation using the combination of a FIS and a VL on a group of patients with known difficult airways requiring in-line stabilization. [14]

### 2.5 C-MAC® Video Laryngoscope

The C-MAC® video laryngoscope is available in the original MACINTOSH blade shapes (sizes 2, 3 and 4), the MILLER shape (sizes 0 and 1), and in the blade shape for difficult airways – the D-BLADE™. The MILLER laryngoscopes correspond with the current MILLER form. The design is in line with the European closed form, which ideally satisfies the stringent demands placed on hygiene and ergonomics.

### 2.6 Rationale

Combined VL and FIS can provide superior conditions for tracheal intubation in patients with head and neck tumors. We hypothesize that the use of the combination technique will improve the time to intubation and also decrease the number of attempts to intubate head and neck patients with known or suspected difficult airways. If our hypothesis is confirmed, a significant large number of patients will benefit (i.e. less trauma, less episodes of hypoxemia and less postoperative sore throat) from the use of this new intubation technique. To test our hypothesis, we plan on conducting a randomized controlled trial using the combination of FIS with VL, comparing it to the use of the FIS alone in patients with known or suspected difficult airways undergoing surgical procedures.

## 3.0 DISCUSSION OF SUBJECT POPULATION

### 3.1 Subject Characteristics

Any male and female patients  $\geq 18$  years of age, undergoing planned surgery.

### 3.2 Inclusion and Exclusion Criteria

#### Inclusion Criteria:

- Ages  $\geq 18$  years of age
- All surgical patients with known or suspected difficult airways that meet at least three (3) of the Difficult Airway criteria [Mallampati III-IV, Neck circumference  $>$  or  $= 40$  cm, Sternomental distance  $< 12$  cm, Thyromental distance  $< 6$  cm, Mouth opening  $< 4$  cm, BMI  $\geq 35$  kg/m $^2$ , Upper Lip Bite Test - ULBT (class III)] or history of radiation to the head or neck area
- American Society of Anesthesiology (ASA) I-IV
- Has provided written informed consent

#### Exclusion Criteria:

- Active bleeding from nasopharynx or oropharynx
- Trismus
- Oral pathology obstructing the glottic view
- Planned awake or nasal intubation
- Neuromuscular Blockade (NMB) contraindicated post-induction
- Emergency endotracheal intubation and patients intubated pre and post-surgery
- Surgical procedures such as Tracheostomy, Laryngectomy, Esophagectomy
- Patient refusal or inability to consent for study participation
- American Society of Anesthesiology (ASA) V
- Pregnant females

### 3.3 Discussion of Subject Population:

Head and neck tumors continue to be very common and a significant number of patients with these tumors present to our practice for surgical care. Wong et al, found a higher incidence of difficult airways in head and neck surgical patients.[8] In the Fourth National Audit Project (NAP4) of the UK, review of cases showed that 39% of all emergent surgical airways were performed in head and neck patients.[3] Therefore, our study is focused on patients who are at increased risk of failed intubation when conventional means are used.

## 4.0 SUBJECT IDENTIFICATION, RECRUITMENT AND CONSENT:

### 4.1 Method of Subject Identification and Recruitment

Subjects will be pre-screened in the patient population scheduled for surgery at MD Anderson Cancer Center's Main OR or Mays OR. Advertisements for study subjects are not anticipated. Once a potential subject has been identified, he/she will be approach in the preoperative holding area and asked to sign the study's informed consent document. Then delegated study staff will perform assessments to verify subject's eligibility, which will be confirmed by the PI or Co-I's prior enrollment. Study Staff will follow institutional policy SOP 04: Informed Consent Process.

#### **4.2 Consent Process**

Subjects will be explained, in detail, the purpose, their role, and study procedures in relation to what's considered research and standard of care (SOC); as well as the potential risks, benefits and alternatives prior to study enrollment. They will be given a consent form to read and if they so choose, to discuss with friends, family, and other clinicians. They will be invited to ask questions and, after all questions are answered to their satisfaction, invited to sign the consent form. The Principal Investigator or designees (with proper delegation of authority) will participate in the consenting process to ensure the subject has full understanding of the procedure and risks. No study-specific procedure will be performed before the consent form is signed.

Subject participation in this investigation is voluntary. Written informed consent is required from all subjects prior to the subject's participation in the investigation. Also, an obtained permission of the faculty anesthesiologist, in charge of the patient's anesthesia care, must also be granted for subject participation. A signed copy of the consent will be given to the subject. While not anticipated, the PI will report any failure to obtain subject consent to the IRB within 5 days of learning of such an event, as required by regulation.

Prior to participating in this investigation, the site will be required to have an IRB-approved Informed Consent Document. Any modifications to the consent must be approved by the IRB of record.

#### **4.3 Costs to the Subject**

None.

#### **4.4 Payment for Participation**

None.

#### **4.5 Return of Individual Research Results**

Not Applicable.

### **5.0 METHODS AND STUDY PROCEDURES**

#### **5.1 Pre-treatment Evaluation**

##### Screening

Patients will be pre-screened for eligibility prior to their scheduled surgical procedure. Eligibility will be verified in the preoperative holding area.

##### Randomization

OnCore will be used to randomly assign eligible study participants to either the control group (N = 60) or the study (intervention) group (N = 60). Additionally, the collection of demographic information will take place before anesthetic and surgical care to acquire baseline data information on: age, gender, height, weight, and BMI. Patients will be randomized after consenting and enrolling into the trial, preoperatively, on their scheduled day of surgery.

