## **10.0 SAMPLE SIZE DETERMINATION AND DATA ANALYSIS**

### **10.1 Sample Size Determination**

A total of 60 evaluable patients will be randomized to each intervention arm. With 60 patients per study arm, a 2-sided chi-square test with alpha = 0.05, and an assumed rate of difficult ETT in one

arm of 30% on the control arm, then a minimum detectable difficult ETT rate of 10% (an absolute difference of 20 percentage points) would be considered statistically significant (nQuery v7) with power of 80%. For each study arm consisting of 60 patients, estimated rates of difficult ETT will be provided using exact 95% CI using the method of Clopper-Pearson. For example, a rate of 25% would provide exact 95% confidence interval limits that do not exceed (0.15 0.38), exact 99% CI limits that do not exceed (0.12, 0.42) using the method of Clopper-Pearson.

In the pursuit of ensuring that a sufficient number of evaluable patients have been enrolled, an adjustment will be made to the total number of randomized patients by adding 20% or an additional 24 patients (12 per study arm). This modification will result in a total sample size of 144 patients. However, the accrual of participants will cease once 60 evaluable patients have been reached on each study arm.

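### The number to be randomised is 120 in the summary and Section 5.1 but up to 144 in Section 10.1; a list built at 60 per arm leaves no room for non-evaluable patients

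*Combined protocol and SAP*

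**What the plan says.** The combined protocol and SAP gives the sample size in four places.

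- **Summary table, study size row:** the row "Study Size (# of patients") gives 120. It does not say whether these are randomised or evaluable patients.
- **Summary table, Brief Analysis Plan:** "A total of 60 patients will be randomized to each intervention arm (a total of n = 120 patients"). The second bullet of the same cell describes the same 60 per arm (120 in total) as evaluable.
- **Section 5.1, Randomization:** OnCore will "randomly assign eligible study participants to either the control group (N = 60) or the study (intervention) group (N = 60").
- **Section 10.1:** the target is 60 evaluable patients per arm. The number randomised is then increased by 20%, or 24 patients (12 per arm): "This modification will result in a total sample size of 144 patients". The section adds that "the accrual of participants will cease once 60 evaluable patients have been reached on each study arm".

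The power statement in Section 10.1 rests on 60 per arm: "With 60 patients per study arm, a 2-sided chi-square test with alpha = 0.05", with "30% on the control arm, then a minimum detectable difficult ETT rate of 10% (an absolute difference of 20 percentage points") and power of 80%. I found no definition of an evaluable patient, and no expected rate of non-evaluability.

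**The concern.** All four places are current text, and the number to be randomised cannot be both 120 and up to 144. Section 5.1 is where someone setting up the OnCore allocation would look, and it attaches 60 and 60 to the act of random assignment. Section 10.1 evidently expects some patients to be non-evaluable, because it provides 24 extra; Section 5.1 leaves no place for them.

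What is at stake is power. The calculation has no spare margin at 60 per arm, so patients lost from a list closed at 60 per arm come straight off the planned power. The approved enrolment ceiling is also unclear while the figures differ.

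**Working it through.** **Inputs (Section 10.1).** Control rate p1 = 0.30, intervention rate p2 = 0.10, two-sided alpha = 0.05 (z = 1.96), uncorrected chi-square test, n = 60 per arm.

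**Step 1: reproduce the stated 80%.**

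Normal approximation with pooled variance under the null, where p̄ = (0.30 + 0.10)/2 = 0.20:

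- Null SE = √(2 × 0.20 × 0.80 / 60) = 0.0730
- Alternative SE = √((0.30 × 0.70 + 0.10 × 0.90) / 60) = 0.0707
- Power = Φ((0.20 − 1.96 × 0.0730) / 0.0707) = Φ(0.804) = 78.9%

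Exact power of the same test is the sum, over all pairs of event counts that give |z| > 1.96, of the product of the two binomial probabilities. At 60 per arm it is 80.2%. The stated 80% is therefore reproduced for 60 *evaluable* patients per arm.

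**Step 2: check the inflation.** 120 × 1.20 = 144, or 72 per arm, as stated. The largest loss that still leaves 60 of 72 evaluable is 12/72 = 16.7%.

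**Step 3: power if only 60 per arm are randomised and none can be replaced.** The loss rates are assumptions; the documents give none.

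| Evaluable per arm | Lost from 60 | Exact power | Normal approximation |
|---|---|---|---|
| 60 | 0% | 80.2% | 78.9% |
| 58 | 3.3% | 79.7% | 77.5% |
| 57 | 5% | 78.9% | 76.8% |
| 54 | 10% | 76.3% | 74.5% |
| 50 | 16.7% | 73.4% | 71.1% |

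Exact power moves in small steps because the counts are discrete (59 per arm gives 80.5%), so a loss of one or two patients per arm is immaterial. The fall becomes noticeable at about 5% to 10%. At the 16.7% that the plan's own allowance would absorb, it is about 7 percentage points (80.2 − 73.4 = 6.8).

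**Step 4: power if up to 72 per arm may be randomised.** With losses up to 16.7% in each arm, 60 evaluable per arm can be reached and power is as planned.

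**Step 5: cost of unequal final arms.** With 120 evaluable in total but split unevenly, exact power is 79.5% to 80.8% at 55/65 and 79.0% to 80.4% at 50/70, depending on which arm is larger.

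**The case against.** The strongest reply is that the plan largely answers itself. Section 10.1 is the dedicated sample-size section, and the Brief Analysis Plan calls the same 60 per arm evaluable, so 120 evaluable with a ceiling of 144 randomised is the natural reading. The study size row does not say randomised at all. I accept this as the likely intent. It does not remove the conflict, because the Brief Analysis Plan and Section 5.1 both attach 60 per arm to randomisation.

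A second reply is that losses should be few. Patients are randomised on the day of surgery (Section 5.1), the primary outcome is determined at intubation (Section 5.4), and a case in which the provider discontinues the protocol procedure counts as a failure (Section 5.3). This stands. A reader might infer that a 60-per-arm list necessarily misses 80% power; the documents do not support that, since it gives 80.2% with no losses and 79.7% with two lost per arm.

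A reader might also infer from the per-arm stopping count that the arm reaching 60 first is closed, so that the last patients are assigned to the other arm without randomisation and predictably. The documents do not say so. Section 10.1 reads equally well as randomising to both arms until each has 60, with one arm going over. Closing an arm while replacing losses is also a different scenario from the power shortfall, which requires that losses are not replaced. The text is silent on the point and should be made explicit, but no number of unrandomised patients can be attributed to the plan.

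Finally, adding 20% is sometimes mistaken for covering a 20% loss. Section 10.1 says only that 20% is added, and 144 is the correct result. There is no arithmetic error.

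**Conclusion.** The inconsistency is real and concerns a figure the trial relies on: 120 randomised in the Brief Analysis Plan and Section 5.1, with 120 as the unqualified study size, against up to 144 randomised in Section 10.1. Its consequence is conditional. If OnCore is set at 60 randomised per arm, exact power stays close to 80% when almost all patients are evaluable. It falls to 78.9% with 5% lost and to about 73% with the 16.7% loss that 144 would cover.

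This assumes the stated rates of 30% and 10%, the uncorrected chi-square test, equal losses in the two arms and no replacement. The actual loss rate is unknown and may be small; because evaluable is not defined, the documents cannot show that it is negligible. The point should be corrected because doing so is almost free, not because the trial is shown to be underpowered.

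**What to change.** 1. In the summary table (study size row and Brief Analysis Plan) and in Section 5.1, replace the current figures with: 120 evaluable (60 per arm), up to 144 randomised (72 per arm).
2. Build the OnCore list to 72 per arm and make sure the approved enrolment ceiling is 144.
3. In Section 10.1, state that both arms stay open to 1:1 random allocation until accrual stops, so that neither arm is closed early, and that accrual does not go beyond 144 if that number is reached first.
4. Define evaluable, since the target and the stopping rule both depend on it.

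The cost is protocol wording and one system setting. The downside is that the final arms may differ somewhat in size, but exact power remains 79.0% to 80.4% even if 120 evaluable patients split 50/70.
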